2.3.1. Risk Assessment

Potential Risk of Clinical Significance	Summary of Data/Rationale for Risk	Mitigation Strategy
Study Intervention LY3016859		
Development of treatment-emergent anti-drug antibodies (TE ADA).	Incidence of TE ADA was 50% after a single dose, and up to 57% after multiple doses.	Collect samples up to 20 weeks after last dose to characterize ADA profile.
IV infusion may be associated with infusion reactions and hypersensitivity reactions.	LY3016859 is a monoclonal antibody that will be administered via IV infusion. Hypersensitivity reactions and infusion reactions may occur during treatment with such agents.	Monitor infusion reactions and hypersensitivity reactions. Guidance on management of infusion and hypersensitivity reactions are in Sections 8.2.1. and 8.2.2.
Dermatological adverse reactions similar to EGFR antagonists	One healthy participant who received a single dose of 1 mg LY3016859 experienced a rash that was considered similar to those associated with EGFR antagonists.	Collect dermatological AEs. Stop dosing for severe dermatological AEs.
Changes in eGFR in participants with diabetic nephropathy (DN)	A modest and non-statistically significant decrease in eGFR was observed in participants with DN who received LY3016859 in Part B of Study TGAB, but not in healthy participants in Study TGAA.	Exclude participants with moderate or severe renal impairment in the study. Short dosing duration. Monitor eGFR and stop dosing if necessary. CCI [REDACTED]
Fetal harm due to in utero exposure	No effects on embryo-fetal development in enhanced pilot embryo-fetal development studies in rats and rabbits. Definitive developmental and reproductive toxicity studies are not yet completed.	Do not enroll women who are pregnant or breastfeeding in studies for LY3016859.
Study Procedures		
Participant may experience increased OA symptoms.	Medications that relieve OA pain will not be allowed until Visit 801.	Rescue medication is permitted. Standard treatment of OA may be restarted after Visit 801 based on investigator discretion.

Abbreviations: ADA = anti-drug antibodies; AE = adverse events; DN = diabetic nephropathy; EGFR = epidermal growth factor receptor; eGFR = estimated glomerular filtration rate; IV = intravenous; OA = osteoarthritis; TE = treatment emergent; TGAA = study I5V-MC-TGAA; TGAB = study I5V-MC-TGAB.

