8.2.3. Adverse Events of Special Interest

Dermatological adverse reactions

EGFR antibodies or EGFR-associated tyrosine kinase inhibitors are associated with various dermatological AEs, including acneiform rashes, xerosis, pruritis, and photosensitivity. Secondary infection can also develop.

Participants should use sun protection during the study period. Dermatological adverse reactions should be managed by the investigator according to standard of care. Discontinuation of treatment may be considered if these AEs do not respond to topical treatment or are widespread (>30% body surface area) or are severe.

If any of these AEs are reported, sites will be prompted to provide additional information.

Renal Function

Changes in eGFR were observed in participants with diabetic nephropathy in Study TGAB (Section 2.2). Such changes were reversible and were not associated with increase in proteinuria. Blood and urine samples will be collected to characterize the effects of LY3016859 on renal function and eGFR will be monitored during the study.

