### **6.12.3. Deaths, Other Serious Adverse Events, and Other Notable Adverse Events**

The general summary of adverse of events is described in the H0P-MC-CPMP SAP Version 5.

Treatment emergent adverse events of special interest will be summarized separately by preferred term. These events include

- infusion site reactions (preferred MedDRA term)
- hypersensitivity and infusion-related reactions
  - Anaphylactic reaction (SMQ)
  - Anaphylactic/anaphylactoid shock conditions (SMQ)
  - Angioedema (SMQ)
  - Hypersensitivity (SMQ)
  - Infusion-related reaction (preferred MedDRA term)
- dermatological adverse events
  - Severe cutaneous adverse reactions (SMQ)
  - Drug reaction with eosinophilia and systemic symptoms syndrome (SMQ)
- abnormal renal function
  - Renal function analyses (MedDRA HLT)
  - Renal failure and impairment (MedDRA HLT)

A large, stylized logo consisting of the letters 'C', 'C', and 'I' in a red, serif font. The letters are set against a solid black rectangular background that covers most of the page.

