**Dermatological**

- Serious or severe dermal reactions

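### The dermatological special-interest group in SAP 6.12.3 does not match the EGFR-type skin events that define the category in protocol 8.2.3

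*SAP*

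**What the plan says.** **Protocol.** Section 8.2.3 lists dermatological adverse reactions as a category of special interest. It says that EGFR antibodies and related kinase inhibitors "are associated with various dermatological AEs, including acneiform rashes, xerosis, pruritis, and photosensitivity", and adds that secondary infection can develop. On data collection it says: "If any of these AEs are reported, sites will be prompted to provide additional information". Severity and extent appear in 8.2.3 only as grounds for considering discontinuation, not as part of what defines the category. The risk table in 2.3.1 cites an EGFR-like rash in one healthy participant, with no severity given, and lists as mitigation: "Collect dermatological AEs. Stop dosing for severe dermatological AEs". Section 7.1 names acneiform rash and gives mild to moderate reactions a role in discontinuation. Section 8.1.1 has the skin examined at each visit.

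**SAP.** Section 6.12.3 sets the reporting rule: "Treatment emergent adverse events of special interest will be summarized separately by preferred term". Under its dermatological heading it lists two standardised MedDRA queries (SMQs): "Severe cutaneous adverse reactions (SMQ") and "Drug reaction with eosinophilia and systemic symptoms syndrome (SMQ"), the latter being DRESS. Neither has a narrow or broad scope stated. A separate group, for hypersensitivity and infusion-related reactions, includes "Hypersensitivity (SMQ"). Section 8 repeats the special-interest analysis at the final lock without adding skin terms. It also provides general tables of treatment-emergent and post-treatment-emergent events by preferred term (alone and within system organ class) and a listing.

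**The concern.** A special-interest table is where a reader looks for a drug's suspected class effect. Here that effect is the rash, dryness and itching known from EGFR inhibition, and the protocol asks sites for extra detail on these events. The SAP instead builds its skin group from one query titled for severe cutaneous reactions and one for a specific systemic drug-reaction syndrome. A treatment arm with frequent mild or moderate acneiform rash could therefore show little or nothing in that group.

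A reader would then have to assemble the class effect from separate preferred-term rows. The protocol fixes the concept, but the mapping to MedDRA terms would be left until the results are visible.

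**Working it through.** The plan states no figure on this point, so the check is mainly a comparison of text.

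**1. What defines the category, and what the SAP group contains**

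| | Protocol 8.2.3 | SAP 6.12.3, dermatological group |
|---|---|---|
| Content | Acneiform rash, xerosis, pruritus, photosensitivity; possible secondary infection | Severe cutaneous reactions SMQ; DRESS SMQ |
| Severity limit | None in the description; any such event prompts extra data | In the title of the first query; the second is a named syndrome with no severity word |
| EGFR-type events named | All of the above | None |

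**2. Whether other groups in 6.12.3 are restricted in the same way.** Infusion site reactions, the Hypersensitivity SMQ and the two renal high-level terms carry no severity word in their titles. The skin group is the only one with an entry titled as severe, and the SAP gives no reason for it.

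**3. Where a mild or moderate EGFR-type event would be reported.** It would appear in the general preferred-term tables and the listing (SAP 8) and possibly under the Hypersensitivity SMQ. If it led to stopping treatment, it would also count under treatment discontinuation due to an adverse event in 6.17, which is not specific to skin.

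**4. Whether those tables give the grouped count.** They do not. Suppose k preferred terms have n₁, …, n_k participants in an arm of size N. The number with at least one of the events is then known only to lie between

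max(nᵢ) and min(Σnᵢ, N),

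because one participant can contribute to several rows. As an illustration only, assume one participant in each of four rows, one row per event type that the protocol names, in the LY3016859 arm (84 planned). The count lies between 1 and 4:

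- 1/84 = 1.2%
- 4/84 = 4.8%

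One participant in the placebo arm (41 planned) is 1/41 = 2.4%. The listing would allow an exact count by hand, but only after someone has chosen the terms.

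**The case against.** **No commitment is broken.** The protocol requires collection and extra site data; it does not promise a grouped table. This stands. The point is a poor fit between the protocol's category and the SAP's group, not a breach.

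**The events are already reported by preferred term, so a list adds little.** This stands in part. A reader might infer that mild and moderate skin events go unreported, and SAP 8 rules that out. What the list adds is the count of participants with at least one event, its breakdown by severity, and a term mapping fixed in advance.

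**The severity wording may be read too strongly.** This also stands. The SAP does not say that the first query filters on graded severity, and it does not call the DRESS entry severe. The mismatch rests on neither query naming the protocol's events.

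**SAP 6.17 has the same restriction.** A reader might extend the criticism to its entry "Serious or severe dermal reactions". The documents do not support that. Section 6.17 is a list of key safety events in which serious or severe thresholds recur, for example for cardiac, hypoglycaemic and hypersensitivity events. The skin entry follows that pattern and agrees with the second half of the mitigation in protocol 2.3.1.

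**Unseen text may fill the gap.** The list in 6.12.3 is introduced in words that may not be exhaustive, a redacted block follows it, and general safety analyses are delegated to the CPMP SAP, which was not available. An additional skin term set cannot be ruled out. Against that, SAP 6.12 places intervention-specific safety considerations in this document, and SAP 8 calls these special-interest events specific to this appendix. If the list is open-ended, the skin group is undefined and still needs wording.

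**Conclusion.** The point holds for SAP 6.12.3. As visible, the dermatological special-interest group does not match the category in protocol 8.2.3 and gives no count of participants with at least one EGFR-type skin event.

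Its size is limited. Neither data collection nor the efficacy analyses are affected, and the events remain in the general tables and listing. No under-count in participants can be stated: that would need the contents of the SMQs, the CPMP SAP and an expected rash rate, none of which the documents give. It would be wrong to conclude that the SAP ignores non-severe skin events or that its skin summary will necessarily be empty of them.

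The conclusion assumes that neither the redacted text nor the CPMP SAP contains a matching skin term list.

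**What to change.** In SAP 6.12.3:

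- Add to the dermatological group a preferred-term list mapped to the events named in protocol 8.2.3 (acneiform rash, dry skin, pruritus, photosensitivity, secondary skin infection), at any severity.
- Report the number and percent of participants with at least one such event, by arm and maximum severity.
- Keep the two existing SMQs as separate rows and state the narrow or broad scope of each.
- Footnote any overlap with the Hypersensitivity SMQ.
- Fix the list before the final lock. If the proof-of-concept (PoC) data have already been unblinded, label it as added after that lock.

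Leave 6.17 as it is. If the CPMP SAP or the redacted text already contains such a list, a cross-reference in 6.12.3 is enough.

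**Cost:** SAP wording and one more table. No new data are needed, because skin is examined at each visit and sites are already prompted for detail. The drawbacks are that some participants may be listed under both the dermatological and Hypersensitivity groups, and that a list added after the PoC lock is not fully prespecified.

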### **6.12.6. Vital Signs and Other Physical Findings**

The analysis of vital sign parameters is described in the H0P-MC-CPMP SAP Version 5.

### **6.12.7. Electrocardiograms**

The analysis of electrocardiograms parameters is described in the H0P-MC-CPMP SAP Version 5.

## **6.13. Subgroup Analyses**

General subgroup analyses are described in the H0P-MC-CPMP SAP Version 5. H0P-MC-OA01 will also consider the following subgroup analyses for the primary efficacy outcome and key secondary outcome.

Subgroup Variable	Categories
Kellgren-Lawrence Grade	Categories: Grade 2, Grade 3, Grade 4  Note: Alternative groupings may be created based on the number of participants classified within each grade (e.g. <3, ≥3)

The subgroup analyses will be conducted using similar modeling approaches as the primary and key secondary analyses. Additional factors in the model are described in the H0P-MC-CPMP SAP Version 5. The treatment difference at the endpoint will be reported within each level of the subgroup factor along with 95% credible intervals. The results may also be presented in a forest plot. Frequentist MMRM will be performed as a sensitivity analysis using the modeling approach described in the H0P-MC-CPMP SAP Version 5.

## 6.14. Protocol Deviations

Participants with study important protocol deviations will be summarized by type of deviation and listed by treatment and investigative site.

Important protocol deviations for the study are described in the H0P-MC-CPMP SAP Version 5 and H0P-MC-OA01 Trial Issue Management Plans.

## 6.15. Interim Analyses and Data Monitoring

Interim analyses will be conducted under the auspices of an Assessment Committee according to the specifications set forth in the protocol. These analyses will be at the CPMP level and will consider data from all ongoing ISAs. Details are provided in the H0P-MC-CPMP SAP Version 5.

There are no additional interim analyses planned for H0P-MC-OA01.

## 6.16. Planned Exploratory Analyses

In addition, a cumulative distribution function of percent change from baseline to endpoint for the WOMAC® pain and physical function subscales will be provided for each treatment group. However, no statistical comparisons will be made between the groups.

## 6.17. Totality of Evidence for Safety

The totality of evidence for safety analysis has been briefly described in the H0P-MC-CPMP SAP Version 5. The key safety events to be considered for H0P-MC-OA01 are listed below by domain:

### General Adverse Event Information

- Serious adverse events related to study treatment
- Study discontinuation due to adverse event
- Treatment discontinuation due to adverse event

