1.3. Schedule of Activities (SoA)

This SoA shows visits and procedures unique to the intervention-specific appendix (ISA) H0P-MC-OA01 (OA01) for LY3016859. Please refer to master protocol H0P-MC-CPMP (CPMP) and the osteoarthritis (OA) disease-state addendum (DSA) H0P-MC-CPMP(1) SoAs for additional information.

H0P-MC-OA01 ISA	Randomization	Double-Blind Treatment				Follow-up			Early Discontinuation	Notes
Visit Number	V3	V4	V5	V6	V7	V801	V802	V803	ED	
Study Week	0	2	4	6	8	12	16	26		
Visit Window (days)		±3	±3	±3	±3	±5	±7	±7		Minimal interval between 2 doses cannot be shorter than 11 days.
Physical examination	X	X	X	X	X	X	X	X	X	Targeted exam for skin, eyes, mouth, lungs and GI tract should be performed at each visit, in addition to any symptom driven exam. Full physical exam should be performed at Visit 803 or ED.
Weight								X		
Vital signs	X	X	X	X	X	X	X	X		Includes respiratory rate, blood pressure, temperature and pulse rate. All vital signs are collected before study intervention infusion on V3-6.
ECG			X		X			X		Single safety ECGs
Study intervention IV infusion	X	X	X	X						1 hour IV administration The timing between randomization and the first IV infusion may be up to, but not longer than 2 business days to reduce participant burden.
Adverse events						X	X	X		
Concomitant medication						X	X	X		
Rescue medication usage reporting						X				If the participant discontinues after V801, this assessment is not needed for ED per the CPMP SoA.
NRS						X				If the participant discontinues after V801, this assessment is not needed for ED per the CPMP SoA.
PGI						X				If the participant discontinues after V801, this assessment is not needed for ED per the CPMP SoA.

H0P-MC-OA01 ISA	Randomization	Double-Blind Treatment				Follow-up			Early Discontinuation	Notes
Visit Number	V3	V4	V5	V6	V7	V801	V802	V803	ED	
Study Week	0	2	4	6	8	12	16	26		
Visit Window (days)		±3	±3	±3	±3	±5	±7	±7		Minimal interval between 2 doses cannot be shorter than 11 days.
WOMAC						X				If the participant discontinues after V801, this assessment is not needed for ED per the CPMP SoA.
C-SSRS						X		X		Use C-SSRS Since Last Visit version.
Self-Harm Supplement Form						X		X		
Self-Harm Follow-up Form						X		X		Required if triggered by the Self-Harm Supplement Form per instructions.
Hematology						X	X	X		
Chemistry		X		X		X	X	X		
Urine Chemistries	X	X	X	X	X	X		X	X	
Urinalysis								X		

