8.1.1. Physical Examinations

Targeted physical examinations of skin, eyes, mouth, lungs and GI tract will be performed at each visit as described in the SoA. Any clinically significant abnormal physical examination findings will be reported as AEs.

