### Cardiovascular

- QTc prolongation: > 60 msec increase
- Serious cardiac disorders adverse event

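### The general SAE line in the safety totality (SAP 6.17) counts only related events, so some serious events judged unrelated fall in no line of that list

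*SAP*

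**What the plan says.** SAP 6.17 introduces its list with "The key safety events to be considered for H0P-MC-OA01 are listed below by domain". The general domain has three lines: "Serious adverse events related to study treatment", "Study discontinuation due to adverse event" and "Treatment discontinuation due to adverse event". The two discontinuation lines take an event of any organ, with no condition on seriousness or relatedness.

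Six further domains follow: cardiovascular, liver, metabolic, renal, dermatological and hypersensitivity. Four of their lines count serious events without stating a relatedness condition. One is "Serious cardiac disorders adverse event"; the others cover hypoglycemia, dermal reactions and hypersensitivity reactions, the last two including severe events as well as serious ones.

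On method, the section says that "The totality of evidence for safety analysis has been briefly described in the H0P-MC-CPMP SAP Version 5". That document is not part of the material reviewed.

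In the protocol, the schedule of activities states "Targeted exam for skin, eyes, mouth, lungs and GI tract should be performed at each visit", and section 8.1.1 adds "Any clinically significant abnormal physical examination findings will be reported as AEs". Of these five sites, only skin has its own domain in SAP 6.17.

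**The concern.** The trial is randomized, placebo-controlled and blind to investigator and participant. The comparison between arms is the evidence on cause, and it needs no case-by-case attribution. A relatedness filter puts an individual judgement ahead of that comparison. Such a judgement tends to follow what is already expected of a drug. Here the protocol names dermatological reactions as expected, while an event at an unexpected site may more readily be called unrelated.

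The filter is also applied unevenly. A serious cardiac event counts whatever its attribution, but a serious lung or gut event counts under the general SAE line only if judged related. The SAP gives no reason for the difference. At stake is whether the summary meant to draw the safety evidence together shows all serious events by arm. Two completed studies are described, in healthy participants and in diabetic nephropathy, so osteoarthritis is a new population for this antibody.

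**Working it through.** The plan gives no figure to reproduce, so the main check is a reading of each line in SAP 6.17.

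**Step 1: which lines can apply.** Take an event of the eyes, mouth, lungs or gut that is not classed as a hypersensitivity reaction. The cardiovascular, liver, metabolic, renal, dermatological and hypersensitivity lines do not apply. Only the three general lines remain.

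**Step 2: enumerate.** Such an event is serious or not, related or not, and leads to discontinuation (of treatment or study) or not: 2 × 2 × 2 = 8 types.

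| Serious | Related | Discontinuation | In a 6.17 line? | After the fix |
|---|---|---|---|---|
| either | either | yes (4 types) | yes | yes |
| yes | yes | no | yes | yes |
| yes | no | no | **no** | **yes** |
| no | yes | no | no | no |
| no | no | no | no | no |

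Five of 8 types are captured now and 6 of 8 after the fix. The type gained is the unrelated SAE without discontinuation. The two types left out are non-serious, and some of those events may be severe. These are counts of event types and say nothing about how often each occurs.

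**Step 3: illustrative size.** The 84 participants planned for LY3016859 come from the protocol synopsis. The rates are assumptions, because the documents give none: a proportion p = 0.02 to 0.06 of participants with an SAE over 26 weeks, of whom a fraction f = 0.1 to 0.3 have one called related.

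- Expected participants with any SAE, 84p: 84 × 0.02 = 1.7 to 84 × 0.06 = 5.0.
- Expected with a related SAE, 84pf: 84 × 0.002 = 0.2 to 84 × 0.018 = 1.5.
- Chance of zero, all SAEs, (1 − p)^84: 0.98^84 = 0.183 to 0.94^84 = 0.006.
- Chance of zero, related only, (1 − pf)^84: 0.998^84 = 0.85 to 0.982^84 = 0.22.

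**Step 4: the window matters.** The SAE line states no window. The lines in 6.17 that do state one (liver, HbA1c, eGFR) use the double-blind period, which is 8 weeks. Assuming a constant rate, p scales by 8/26 to 0.0062 to 0.0185, and pf to 0.0006 to 0.0055.

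- Chance of zero, all SAEs: about 0.60 to 0.21.
- Chance of zero, related only: about 0.95 to 0.63.

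**Step 5: what this does not measure.** Steps 3 and 4 compare all SAEs with related SAEs. The loss to the list is smaller, because unrelated SAEs that are cardiac, hypoglycemic, dermal or hypersensitivity events, or that cause discontinuation, are counted elsewhere in it. No figure in the documents allows that remainder to be isolated.

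**The case against.** The case on the other side has several parts.

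- **A reader might infer that the whole totality counts only related SAEs.** It does not. Four domain lines state no relatedness condition, and the discontinuation lines take any adverse event. Some events at the examined sites can also count as hypersensitivity: protocol 6.1.1.2 names bronchospasm, angioedema and throat irritation as signs of an infusion reaction. This objection stands, and the point is limited to one line.
- **A reader might infer that a safety signal is hidden.** The documents do not support that. SAP section 8 plans an SAE summary and listing, and treatment-emergent and post-treatment events by preferred term and organ class, with no relatedness filter stated. Section 6.19 reports SAEs by treatment group. Clinically significant examination findings enter these outputs as adverse events. This also stands.
- **A reader might infer that the visit-by-visit examinations oblige 6.17 to carry eye, mouth, lung and gut lines.** They do not. The examinations are monitoring. Neither the protocol's risk table nor the lists of events of special interest (protocol 8.2.3, SAP 6.12.3) name such a category. Those lines are a matter of preference.
- **General and domain lines may use different filters, and attribution is made blind.** It is true that no mechanism favoring one arm is shown, and the SAP does not say who judges relatedness. But a blinded filter still removes events from a sparse comparison, and the SAP does not explain why it applies to this line alone.
- **The master SAP may add events or define how the list is used.** This cannot be checked and remains a limit on the conclusion.
- **Changing the list now may be post hoc.** Section 6.17 was added in SAP Version 3, before PoC unblinding. Version 4 was approved before the final lock and appears to follow the PoC lock. The section 8 list for the final lock does not name the totality analysis. This calls for labeling and is no reason to keep the filter.

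**Conclusion.** The point holds in a narrow form. As written, SAP 6.17 leaves out an SAE that is outside the cardiac, hypoglycemia, dermal and hypersensitivity categories, is judged unrelated, and leads to neither treatment nor study discontinuation. The omission affects the totality summary and not safety reporting as a whole.

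The textual conclusion rests only on the wording of 6.17, subject to the master SAP adding nothing that fills the gap. The probabilities above are illustrative, since they depend on assumed SAE and relatedness rates and, for the 8-week version, on a constant rate. They show that a related-only line is more likely to be empty. They also show that over 8 weeks an unfiltered line would often be empty too, so the gain from the change is real but modest.

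**What to change.** In SAP 6.17, replace the general SAE line with *Treatment-emergent serious adverse events, regardless of relatedness*, compared by arm, and keep related events as a sub-line. State the window the line covers, because the chance of an empty line depends on it. If the change is made after the PoC lock, say so in the revision history and wherever the result is reported. Confirm against the master SAP that the change fits the totality method described there.

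Separate serious-or-severe lines for eye, mouth, lung and gut events are optional. They would be needed only if the sponsor wants severe, non-serious events at those sites in the list, which the main change does not add.

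The cost is a wording change and a table row, from adverse-event data already collected. The downside is more background events in both arms.
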